15.0 DATA AND PROTOCOL MANAGEMENT

- 15.1 PROTOCOL COMPLIANCE Patients will be reviewed weekly during admission by the study investigators who will score the patient for standard endpoints. After discharge they will be reviewed at least once a month.

- 15.2 DATA ENTRY Data must be entered into the transplant database on a regular basis. Flowsheets will be kept for clinical and data collection purposes. A brief explanation for required but missing data should be recorded as a comment.

- 15.3 ACCURACY OF DATA COLLECTION The Study Chairman will be the final arbiter of toxicity should a difference of opinion exist.

15.4 REPORTING TO IBMTR AND NMDP

As is customary in most transplant centers we plan to provide data to the International Bone Marrow Transplant Registry. We will also provide outcome data on unrelated donor recipients to NMDP as requested by that organization. Appropriate language will be included in the consent forms for this purpose.

16.0 CRITERIA FOR REMOVAL FROM PROTOCOL

- 16.1 At patient request.

- 16.2 Clinical progression. Such patients may be treated on other treatment protocols or at the investigator's discretion. Such patients will continue to be monitored for survival and, may be asked to continue to provide specimens for studies of minimal residual disease and immune reconstitution as other treatments are recommended.

17.0 REPORTING REQUIREMENTS

Any unexpected life-threatening and serious (grade 3 or 4) toxicity will be reported immediately to the Study Chairman. The Chairman will be responsible for notifying the Surveillance Committee.

Expected toxicities are those listed in the consent form and include regimen-related toxicities, myelosuppression, opportunistic infections such as CMV reactivation, or GVHD. These will not be routinely reported to the IRB even if they require admission.

On the other hand, such toxicities will be monitored by the PI and the transplant team and reported regularly at the High Risk Protocol Committee of the cancer center.

All deaths that are not due to disease recurrence will be reported to the IRB.

APPENDIX A: Treatment plan

Day	Clonazepam	Fludarabine	Busulfan	Bu pharmacokinetics	Campath
Test Dose					
-	PO				
-	PO		0.5 mg/kg	x 6	
-	PO				
Treatment Doses					
-7 PO		25 mg/m ²			20 mg
-6	PO	25 mg/m ²	AUC based	x 5	20 mg
-5	PO	25 mg/m ²	AUC based		20 mg
-4	PO	25 mg/m ²	AUC based	(x 5*)	20 mg
-3	PO	25 mg/m ²	AUC based	x 5*	20 mg
-2	PO				
-1					
0					

Comments:

Busulfan administration has been associated with a low incidence of seizures and dilantin is routinely used for seizure prophylaxis. Dilantin use is discouraged in this protocol because exposure to dilantin can affect Busulfan metabolism.⁶⁹

We recommend benzodiazepines e.g clonazepam (klonopin ®) 1 mg PO TID

Scheduling:

Busulfan test dose:

The test dose can be scheduled any day within 8 days prior to admission. Clonazepam will be started with an evening dose, the day prior to the test dose and two doses one day after test dose. Busulfan test-dose will be based on actual body weight and will be accompanied by extensive pharmacokinetic studies. This dose will be given as an outpatient.

Patients will be admitted in the evening of day -8, to start fludarabine on day -7

Fludarabine:

Fludarabine dosing will be based on actual body weight. Fludarabine will be infused over 30 minutes before busulfan treatment dose.

Busulfan treatment doses:

On each day of treatment, busulfan will be administered through a fresh infusion line at a steady rate over 3 hours. Infusion will start in the morning around 8 AM and will be completed around 11 AM, allowing ample time for pharmacokinetic sampling in the afternoon.

*Pharmacokinetic studies will be performed on the day 1 dose and again on the day 4 dose. For logistical reasons (week-end, holidays), day 3 pharmacokinetics may be performed instead of day 4.

Campath

All patients will receive premedication for Campath as per current standards at the UC transplant unit.

18.1.1 Dose escalation schedule (see also statistical plan)

The targeted AUC of busulfan will be escalated and de-escalated in an up and down design to achieve a dose where less than 4 of 12 patients have a DLT.

Target AUC's are the following:

Dose level 0: 4800 mcgr.min/L.dose

Dose level 1: 5800 mcgr.min/L.dose

Dose level 2: 6800 mcgr.min/L.dose

Dose level 3: 7800 mcgr.min/L.dose

Dose level 4: 8800 mcgr.min/L.dose

Dose level 5: 9800 mcgr.min/L.dose

We do not anticipate further dose-escalation beyond dose level 5. If such dose-escalation were to be considered, we would resubmit an amended protocol to the IRB.

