The phase I portion of the trial will use the modified continual reassessment method (CRM) to determine the maximum tolerated dose (MTD). The primary endpoint for the phase II trial will be the disease-free survival rate (DFS) at one year, and a Simon two-stage design will be used to test the null hypothesis that the one-year DFS rate is 25% against the alternative that it is at least 40%. Adverse events will be monitored, and multiple regression, logistic regression, and Cox regression analyses will be performed to examine the association between GSTA1 enzymatic activity and busulfan metabolic rate, GSTA1 enzymatic activity and the incidence of toxicity, and pharmacogenomic predictors of DFS, respectively.

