14.0 STATISTICAL CONSIDERATIONS

Phase I

For the phase I portion of the study, we will employ the modified continual reassessment method (CRM) to determine the maximum tolerated dose (Faries, 1994; Goodman et al., 1995)^{61,62}. Dose-limiting toxicity (DLT) will be as defined under 13.0 and, occurring within the first 21 days after transplant. Dose cohorts of size three will be utilized and we will target the 25th percentile of the tolerance distribution, i.e., the dose level producing DLT in 25% of the patient population. Briefly, the modified-CRM design utilizes a one-parameter, logistic regression model for the dose-toxicity curve

$$p(x) = \frac{\exp(3 + \beta x)}{1 + \exp(3 + \beta x)}, \quad (1)$$

where $p(x)$ is the probability of DLT at dose level x . A prior distribution is assumed for the parameter β and the first three patients are assigned to the lowest dose level. After outcomes are observed for these patients, the posterior distribution for β is calculated and the estimated toxicity probabilities are updated. The next cohort of patients are assigned to the dose level closest to the targeted percentile, with the restriction that doses can not be escalated more than one level at a time. Enrollment is continued until a predetermined total number of patients have been studied, whereupon the MTD is derived based on the final, estimated dose-toxicity curve.

In our trial, the first cohort of three patients will be enrolled at dose level 0 and after all three of these patients have been followed to day 60 the observed number of DLTs will be used to update the posterior distribution and determine the dose level for the succeeding cohort. Since we anticipate an accrual rate of approximately three patients per month, it is likely that all three patients from a given cohort will not have been followed to 60 days before the next eligible patient becomes available. In this case we will assign such patients (termed *excess* patients) to the current dose level; once the original three patients pass the 60-day landmark, we will update the prediction probabilities using all available data. However, so as not to bias the procedure, if *excess* patients have not been followed for a full 60 days, we will not include their toxicity outcomes in the updated analysis, even if a DLT has been observed. A total of 30 patients will be enrolled in the phase I trial.

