Because delayed VOD (day 30 and day 60) of moderate severity has been observed in two of the 12 initial patients on study, the observation period for successive patients will be extended to 60 days before dose escalation. This will lead to accrual of a higher number of patients per dose level and therefore we anticipate up to 50 patients in the phase I trial.

Addendum June 2006: Pharmacokinetics for the initial 20 patients was performed in the cancer center core facility at UC. For logistical reasons and for more intensive monitoring another laboratory will be

used and technical modifications in sampling have been introduced. Therefore accrual will resume at dose level 0. This will result in accrual of an additional 20 patients to the protocol.

Phase II

The primary endpoint for the phase II portion of the trial is the disease-free survival rate (DFS) at one year defined as the proportion of patients alive and without evidence of recurrence one year after the initiation of therapy. All patients will be followed for a minimum of one year and we will test the null hypothesis that the DFS rate at twelve months is $\leq 25\%$ versus the alternative that it is at least 40%. A Simon (1989), optimal two-stage design will be employed in which 29 patients are enrolled in the first stage.⁶³ (Patients treated at the MT D during the phase I portion of the study will be included in the phase II trial.) If the number alive and without evidence of recurrence at twelve months is 7 or fewer, the study will be terminated for lack of efficacy. Otherwise, subject to the monitoring described below for graft failure, liver toxicity, and GVHD, an additional 43 patients will be enrolled for a total of 72. If 22 or fewer patients are disease free at 12 months the regimen will be rejected, whereas if 23 or more of the total 72 patients ($> 32\%$) are disease free, the regimen will be considered worthy of further evaluation in phase III trials. This design has an α -level of 10% and a power of 90% under the alternative hypothesis that the true 12-month DFS rate is 40%. The probability of early termination when the 12-month DFS rate is 25% is 0.56. However, to avoid a long suspension of the trial, accrual will continue into the second stage while the one-year outcomes in the 29 first stage patients are being accumulated.

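### Appendix A gives a different MTD rule from section 14.0, and both dosing tables print the target AUCs in a unit about 246-fold too small

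*Combined protocol and SAP*

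**What the plan says.** **Escalation rule.** The abstract states: "The phase I portion of the trial will use the modified continual reassessment method (CRM) to determine the maximum tolerated dose (MTD"). Section 9.1.3 names the same method. Section 14.0 gives the detail. Patients enter in cohorts of three, and "we will target the 25th percentile of the tolerance distribution", which 14.0 explains as a 25% DLT rate. Then "The next cohort of patients are assigned to the dose level closest to the targeted percentile", with escalation limited to one level at a time. "Enrollment is continued until a predetermined total number of patients have been studied", and the MTD is read from the final fitted curve.

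Appendix A, 18.1.1, says something else: the target AUC is "escalated and de-escalated in an up and down design to achieve a dose where less than 4 of 12 patients have a DLT". Its heading refers the reader to the statistical plan. The section is current text, not a log of changes.

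**Unit of the target AUCs.** Section 5.3.4 gives the starting daily target as 4800 µmol·min, the test-dose exposure as about 600 µmol·min, and the resulting cumulative exposure as 19800 µmol·min. The tables in 9.1.3 and 18.1.1 start from the same 4800 but print every level in micrograms, up to "Dose level 5: 9800 mcgr.min/L.dose".

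**The concern.** The MTD is the first objective. It fixes the phase II dose, and 14.0 counts phase I patients treated at the MTD in the phase II sample. The protocol should therefore state one rule for finding it. A CRM that uses all the data through a model and a count criterion at a single level are different algorithms, even if both aim near 25%. The reference in 18.1.1 to the statistical plan does not settle which governs, because that plan says something different. The choice still mattered after the June 2006 addendum to 14.0: "Therefore accrual will resume at dose level 0".

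The unit matters because the two tables are where the six dose levels are defined, and treatment doses are calculated to reach those targets.

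**Working it through.** **1. The plan's own exposure figure.** Inputs from 5.3.4: four daily doses, 4800 per dose, about 600 from the test dose.

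- 4 × 4800 + 600 = 19800, exactly as stated in µmol·min.
- The comparison study also fits: 4 × 4897 = 19588, against a stated value of about 19600.

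So 4800 is meant in µmol·min.

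**2. The unit as printed.** The documents give no molar mass for busulfan. I assume 246.3 g/mol and show 240 to 250 as a range. I read µmol·min in 5.3.4 as per litre.

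- Level 0: 4800 / 246.3 = 19.5 µmol·min/L (range 19.2 to 20.0).
- Level 5: 9800 / 246.3 = 39.8 µmol·min/L (range 39.2 to 40.8).
- Against the test dose: 19.5 / 600 = 3.2%; 39.8 / 600 = 6.6%.
- Course total at level 0: 4 × 19.5 + 600 = 678 instead of 19800.
- Dose, using the linear pharmacokinetics and the 0.5 mg/kg test dose of 5.3.4: the intended target scales to 0.5 × 4800 / 600 = 4.0 mg/kg/day; the printed one to 0.5 × 19.5 / 600 = 0.016 mg/kg/day.

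**3. The Appendix A criterion alone.** A level passes if X ≤ 3, with X binomial, n = 12.

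| True DLT rate | P(pass) | P(fail) |
|---|---|---|
| 20% | 0.795 | 0.205 |
| 25% | 0.649 | 0.351 |
| 30% | 0.493 | 0.507 |
| 33⅓% | 0.393 | 0.607 |

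The largest passing result, 3/12, equals the CRM target, but its exact 90% confidence interval runs from 7% to 53%.

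**4. A case that needs no model assumptions.** Suppose 4 of 12 patients have a DLT at level 0. Under Appendix A no level is acceptable. Under 14.0 there is no lower level and no phase I toxicity stopping rule, so enrolment continues to the planned total.

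**5. Illustration with the CRM.** Section 14.0 gives neither coded doses nor a prior, so both are assumed. Equation (1) is used unchanged, with x_j = logit(p_j) − 3. The next level is the one whose posterior mean DLT probability is nearest 25%, rising by at most one level. Assumed starting DLT probabilities for levels 0 to 5 (skeletons):

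- A: .05/.10/.18/.25/.35/.45
- B: .05/.12/.25/.40/.55/.65
- C: .10/.18/.25/.35/.45/.55
- D: .15/.25/.35/.45/.55/.65
- E: .02/.05/.10/.18/.25/.35
- F: .05/.25/.40/.50/.60/.70

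Assumed priors for β: Exponential(1), and Gamma with mean 1 and shape 5 or 20. That makes 6 × 3 = 18 settings.

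| Data | CRM | Appendix A |
|---|---|---|
| 4/12 at level 0 | stays at level 0 in 18 of 18 (estimated DLT 0.210 to 0.351) | level 0 not acceptable |
| 0/3 at level 0, 4/12 at level 1 | keeps level 1 in 18 of 18 (estimated DLT 0.212 to 0.320) | rejects level 1 |
| 1/3 at level 0, 4/12 at level 1 | steps down in 14 of 18, stays in 4 | rejects level 1 |

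The rules part in the first two cases and mostly agree in the third.

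**The case against.** The governing rule can be inferred. Three places name the CRM, the outlying sentence sits under a heading that refers to the statistical plan, and 3/12 matches the 25% target. On that view this is an editorial slip. The inference about intent is fair, but the two texts still conflict.

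The numbers can also be challenged:

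- **The 0.351 and 0.393 describe Appendix A alone.** This stands: they measure its error, not its disagreement with the CRM, which also misses. In a simulation of the 14.0 CRM (30 patients, the same six skeletons, Exponential(1) prior, assumed true DLT rates .05/.15/.25/.38/.50/.60, 300 runs each), it chose the level truly at 25% in only 46% to 51% of trials. The figures also treat the criterion as a fixed 12-patient test, and 18.1.1 does not say when the 12 are counted.
- **Appendix A gives no instruction when no level qualifies.** This stands, so any stop at 4/12 on level 0 is inferred. Oversight also exists: a monitoring committee (14.0, phase II text) and regular toxicity reports to the high-risk protocol committee (17.0). Neither is a numeric phase I boundary.
- **The 18 of 18 depends on the skeletons.** This stands. With .20/.30/.40/.50/.60/.70 or .25/.35/.45/.55/.65/.75, the CRM steps down on 0/3 and 4/12 under all three priors (6 of 6), as Appendix A would. The case shows only that the rules can differ.
- **The unit error is no realistic dosing hazard.** Largely right. Every printed target lies below the test dose's exposure, 5.3.4 shows the intended unit, and 20 patients had already had pharmacokinetics done. The dose levels are nevertheless wrong as printed.

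**Conclusion.** Both conflicts hold and should be fixed. The protocol carries two rules for its first objective, and they can reach different decisions on the same data. The case of 4/12 at level 0 shows this without any assumed skeleton or prior; how often the rules would differ in practice cannot be settled, because 14.0 gives no coded doses or prior. That the Appendix A sentence is leftover is an inference, since the documents do not show its history.

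The unit error affects all six levels in both tables and is about 246-fold (240 to 250 across the assumed molar masses). That µmol·min is intended rests on the plan's own arithmetic, not on the molar mass. Harm from the unit is unlikely. Neither conflict changes a stated sample size.

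**What to change.** 1. In Appendix A, 18.1.1, delete the up-and-down sentence with its 4-of-12 criterion. Put in its place: *Target daily AUC is assigned, and the MTD chosen, by the modified CRM in section 14.0, with a target DLT probability of 25%.* If the sponsor wants a toxicity bound at level 0, state it once in 14.0 as a stopping rule, not as a second definition of the MTD.
2. In 9.1.3 and 18.1.1, change the unit of all six levels to µmol·min/L per dose.
3. For consistency, add the missing per-litre to 5.3.4 and reconcile the historical threshold of 1500, which 5.3.2 gives in µmol·min and 5.3.3 in mg·min/L. These are background sections and do not affect the two corrections above.

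Optionally, record in 14.0 the coded doses and prior actually used, without choosing new ones after seeing data.

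The cost is a text amendment: the two necessary corrections change one sentence and one unit in two tables. No patients, visits or procedures are added.

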18.1.2 Bone marrow/stem cell infusion

On day 0 the stem cell product will be infused according to BMT unit policy.

Bone marrow, PBSC will not be further processed except in the case of ABO-incompatibility. In such instances, red blood cells will be removed from bone marrow products or from PBSC products containing excessive amounts of RBC (as per transplant policy).

All stem cell products procured through the NMDP will be done so in strict compliance with the protocols, policies, and procedures established by the NMDP.

18.1.3 GVHD prophylaxis

Tacrolimus 0.03 mg/kg/day IV CI over 24 hr from 4 PM day -2 until engraftment or when patient is able to take PO, then tacrolimus 0.09 mg/kg PO in 2 divided doses. Tacrolimus should be given at full dose to maintain levels of 5-15 ng/mL through day 100. Thereafter tacrolimus will be tapered by 20% every week unless the patient has developed GVHD.

18.1.4 Supportive care:

Infection prophylaxis and supportive care will be as BMT unit policy. No routine growth factor support will be administered. Growth factor support will be considered in case of delayed engraftment (ANC < $0.5 \times 10^9/L$ on day 12)

18.1.5 Back-up bone marrow harvest (only for recipients of mismatched or unrelated donor transplants)

For patients transplanted in remission, a backup bone marrow or peripheral blood stem cell collection will be considered within two weeks prior to hospital admission as long as the overall marrow cellularity is greater than 30%. All backup harvests will be cryopreserved after processing for buffy coat without any further manipulation. The backup stem cells will be given if deemed clinically necessary in the event of failure to engraft by day +35, graft rejection after day +35, or graft failure after day +35.

